Length of hospital stay will be recorded for all patients following the surgical procedure with the day after surgery defined as postoperative day one. The medical record will be reviewed following discharge to determine if hospital discharge date was dependent on POUR or other reason (e.g. uncontrollable pain, mobility requiring physical therapy or inpatient rehabilitation, or other medical complications delaying discharge).

In addition to the primary and secondary outcome measures, baseline characteristics will be collected on all patients via the medical record including age, height and weight, past history of postoperative urinary retention or diagnosis of benign prostatic hyperplasia (not on treatment), length and type of surgery, estimated blood loss during surgery, total intravenous fluids administered perioperatively, time to oral analgesic use (in hours), total analgesic use during the postoperative period, time to first postoperative mobility (in hours), and any adverse events thought to be related to administration of the study medication. These variables will be used as baseline comparisons between the two groups to ensure homogeny and be used in statistical adjustment if differences between the groups are significant after randomization.

Unanticipated events:

There is the potential for patients to experience urinary retention as outpatients after inpatient urinary retention has resolved. This is quite unusual to occur after urinary retention has resolved as defined above and may indicate the patient needs further investigation by a urologic surgeon. Patients will be counseled by nursing staff prior to dismissal regarding the signs and symptoms of urinary retention and directed to seek medical attention with appropriate urology referral should the treating physician deem this is appropriate.

Patients experiencing prolonged postoperative urinary retention (> 5 days) will be seen by the urology consult service for recommendations regarding further investigation and treatment. The study group designation may be broken at this point to determine which group the patient is in regarding treatment medication if deemed necessary by the urology consult service to guide further treatment.

Patients experiencing severe adverse events such as profound hypotension, arrhythmia, or allergic reaction will be evaluated by the primary neurosurgical team with appropriate intervention or consultation as deemed necessary.

Quality Control:

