The primary outcome measure of incidence of POUR was used to calculate sample size. Data gathered from multiple series suggests that postoperative urinary retention occurs in 2-69% of patients undergoing a variety of surgical procedures, with 38% occurring in neurosurgical patients undergoing simple decompressive spinal procedures. Using 20% (P2=0.20) as a conservative estimate of incidence, an effect size of 10% for the primary outcome variable (P1=0.10) would be clinically meaningful. Thus, P2-P1 = 0.10. Because incidence of urinary retention is a binary categorical variable, a chi-squared test can be used to compare groups. Based on a type I error rate of 0.05 (α), a type II error rate of 0.20 (β), and power of 0.80 the estimated sample sizes needed for each group are as follows. For a one sided type 1 error, there would need to be 175 subjects in each group. For a two-sided type 1 error there would need to be 219 subjects in each group. A one-sided test of significance is reasonable in this study because an increase in incidence of POUR experienced in the tamsulosin treated group is not anticipated and would not add additional useful information in terms of using tamsulosin for POUR. Thus, a reasonable estimate for sample size is 175 subjects in both the treatment and control groups. Furthermore, with 175 patients per arm, there would be 87% power to detect a 1 day difference in the duration of urinary retention and duration of hospital stay with a 1-sided significance level of 0.05 (this assumes an effect size for this secondary outcome variable of 0.30 [1 day difference in means/pooled standard deviation estimate of 3.33]).

Role in Project:

[name]: Co-Principalinvestigator for the study, responsible for study design, study implementation, data collection, reporting of adverse events, and manuscript preparation.

[name]: Co-investigator responsible for assisting in study implementation, data collection, and manuscript preparation.

[name]: Co-investigator responsible for IRB application, Informed Consent form, and pharmacy liaison.

[name]: Statistician responsible for overseeing statistics performed by the co-PI as part of the CTSA BERD program.

[name]: Member of the Office of Research and Regulatory support who will be assisting with the Investigational New Drug application and corresponding with the FDA.

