Studies using nonspecific alpha-1-adrenergic receptor blockade have shown benefit in reducing POUR with minimal adverse effects.^{12,13,30-37,39} Tamsulosin is regarded as being safer with respect to cardiovascular side effects than earlier generation alpha-1-antagonists due to its uroselective nature.^{45,49,50} The potential benefit of reduced incidence and duration of POUR, reduced morbidity associated with repeat intermittent catheterizations, reduced incidence of UTI, and reduced hospital length of stay outweigh the risks associated with administration of this medication.

The primary risk to human subjects taking tamsulosin in this study is postural or orthostatic hypotension, estimated to occur in 0.2% of patients taking the 0.4 mg daily dose of the drug. All patients will be regularly monitored with respect to blood pressure, heart rate, and rhythm according to existing standard postoperative procedures in place on the neurosurgical wards. Per the postoperative neurosurgery protocol, all patients are ambulated with the assistance of nursing staff until they are deemed safe for independent ambulation. Abnormal ejaculation was reported in 8.4% of patients taking the 0.4 mg daily dose. This risk should be minimal in the study given the short duration of time taking the study medication and decreased likelihood of sexual activity in the immediate postoperative period. There have been some reports of intraoperative floppy iris syndrome during cataract surgery during the short time they are on the study medication. Allergic type reactions have been reported rarely. Patients will be informed as to the signs and symptoms of

allergic reactions. Priapism has also been reported as a rare risk (less than 1 in 50,000). Male patients will be informed about the seriousness of this condition.

Other adverse reactions include headache, dizziness, rhinitis, infection, asthenia, back pain, diarrhea, pharyngitis, chest pain, cough increased, somnolence, nausea, sinusitis, insomnia, libido decreased, tooth disorder, and blurred vision. Postmarketing experiences have also shown infrequent reports of dyspnea, palpitations, hypotension, atrial fibrillation, arrhythmia, tachycardia, skin desquamation including reports of Stevens-Johnson syndrome, constipation, and vomiting. All risks are taken directly from the official FDA drug information sheet.¹⁶

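### The one-sided 0.05 level is justified for POUR incidence only but is also applied to length of hospital stay, where a two-sided test keeps about 80% power at 175 per arm

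*Combined protocol and SAP*

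**What the plan says.** All of the following is in the combined protocol and SAP.

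- **Reason for one-sided testing** (Analysis of the Data, sample-size paragraph): "A one-sided test of significance is reasonable in this study because an increase in incidence of POUR experienced in the tamsulosin treated group" is not expected and would tell the investigators nothing useful about the drug for POUR. No other reason is given.
- **Level for length of stay** (same paragraph): "87% power to detect a 1 day difference in the duration of urinary retention and duration of hospital stay with a 1-sided significance level", set at 0.05, for 175 per arm. The assumption is "an effect size for this secondary outcome variable of 0.30 [1 day difference in means/pooled standard deviation estimate of 3.33".
- **Test for length of stay** (Analysis of the Data, first paragraph): a nonparametric test such as the Wilcoxon rank sum is foreseen because the data are expected to look non-normal. Sidedness is not stated.
- **Direction** (Hypothesis 3 and Specific Aim 2): stay is expected to fall, as a consequence of less and shorter POUR.
- **Other influences on stay** (Outcome Measures): the discharge date may depend on pain, mobility or "other medical complications delaying discharge".
- **Drug risk** (Adverse Events): "The primary risk to human subjects taking tamsulosin in this study is postural or orthostatic hypotension", which the same sentence puts at 0.2% of patients on the study dose.

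**The concern.** The argument for one-sided testing has two parts: the opposite result is not expected, and it would not be useful. Both are made for POUR incidence. The plan makes neither for length of stay, and the second does not carry over. The Rationale and Significance sections rest the economic case on shorter stays, so evidence of a longer stay would bear directly on whether to adopt the drug, however unlikely it is thought to be.

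Two things are at stake. A one-sided 0.05 test puts the whole error rate on the favourable side, so a false claim of shorter stay has a 5% chance instead of the 2.5% that a two-sided 0.05 test allows. Such a test also treats an observed lengthening, of any size, in the same way as no difference.

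**Working it through.** **Inputs.** From the sample-size paragraph: n = 175 per arm ("a reasonable estimate for sample size is 175 subjects in both the treatment and control groups"), difference 1 day, SD 3.33, alpha 0.05. Subject Recruitment and Retention says recruitment continues until 175 per group have completed, so no dropout adjustment is applied.

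**Step 1: reproduce the stated 87%.**
- Standard error of the difference = 3.33 × √(2/175) = 0.356 day.
- Standardised difference = 1/0.356 = 2.809.
- One-sided power = Φ(2.809 − 1.645) = Φ(1.164) = 87.8%.
- The noncentral t gives 87.7% (87.6% with the effect size set to exactly 0.30).

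The plan's figure is reproduced, which confirms that it is a one-sided comparison of means using all 175 per arm.

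**Step 2: the same comparison two-sided at 0.05.**
- Power = Φ(2.809 − 1.960) = Φ(0.849) = 80.2%.
- The noncentral t gives 80.0% (79.9% at effect size 0.30).
- Check by sample size: n = 2 × (1.960 + 0.842)² × 3.33² / 1² ≈ 174.1, so 175 per arm.

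The planned sample size is therefore just what 80% two-sided power needs for this outcome. The loss is 87.7 − 80.0 = 7.7 points. The observed mean difference needed for significance rises from 1.645 × 0.356 = 0.59 day to 1.960 × 0.356 = 0.70 day.

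**Step 3: the Wilcoxon test.** Multiply n by the asymptotic relative efficiency, which is 0.955 on normal data and at least 0.864 for location shifts.

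| Test | One-sided 0.05 | Two-sided 0.05 |
|---|---|---|
| t-test | 87.7% | 80.0% |
| Wilcoxon, efficiency 0.955 | 86.4% | 78.4% |
| Wilcoxon, efficiency 0.864 | 83.3% | 74.3% |

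**Step 4: where the one-sided saving arises.** The plan gives 175 per group one-sided and 219 two-sided for POUR incidence. The saving of 219 − 175 = 44 per group belongs to the primary outcome. Length of stay does not need it.

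**Step 5: why 80% cannot replace 87% for both outcomes.** Duration of POUR is compared only among patients who have it. On the plan's rates that is 0.20 × 175 = 35 on placebo and 0.10 × 175 = 17.5 on tamsulosin. At effect size 0.30 the standardised difference is 0.30/√(1/35 + 1/17.5) = 1.02. Noncentral-t power is about 26% one-sided and 17% two-sided.

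**Step 6: can the named drug risk lengthen mean stay by a day?** 0.002 × 175 = 0.35 expected cases of orthostatic hypotension. A 1-day shift in the mean by this route alone would need 175/0.35 = 500 extra days per affected patient. It cannot.

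**The case against.** **A directional rationale exists.** Hypothesis 3 predicts a decrease, Aim 2 places stay downstream of POUR, and one-sided testing is called reasonable for the study as a whole. This stands in part: the expected direction is stated. It does not say why the opposite result would be uninformative, which is the other half of the plan's own argument.

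**The one-sided level for stay sits in a power statement, not in an analysis rule.** This stands. A reader might infer that the plan forbids ever declaring a longer stay. The documents do not say so, because the paragraph on tests is silent on sidedness and nothing prevents an observed lengthening from being reported. The supportable statement is that the only level given for this outcome is one-sided. If a two-sided test was meant, the 87% is the wrong figure for it, so the text needs correcting either way.

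**The harm route is weak.** This stands too. A reader might link hypotension with the listed causes of delayed discharge and conclude that a longer stay is likely. The 0.2% rate does not support that (Step 6), the other adverse reactions that could slow mobilisation, such as dizziness and asthenia, are listed without rates, and Outcome Measures does not tie the causes of delay to tamsulosin. The point does not depend on that route.

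**Length of stay is secondary.** True, and this limits the weight of the point. It is still a named hypothesis and part of a specific aim.

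**Conclusion.** The point holds in a limited form. The reason offered for one-sided testing covers POUR incidence only, yet one-sided 0.05 is the only level stated for length of stay. Moving to two-sided 0.05 halves the false-positive rate for a shorter-stay claim, from 5% to 2.5%, and makes the test sensitive in both directions. It costs about 8 points of stated power.

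The 80% rests on the plan's 1 day and SD of 3.33, on 175 completers per arm and on a comparison of means. For the Wilcoxon test the plan anticipates, about 78% applies to normal data and about 74% at the lower efficiency bound; the true figure depends on the shape of the stay distribution, which the documents do not give. A reader might carry the 80% over to duration of POUR because the plan quotes one power figure for both. That would be false: duration is measured only in patients with retention. The primary analysis is not affected.

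**What to change.** 1. In the first paragraph of Analysis of the Data, state that length of hospital stay is tested two-sided at 0.05 and reported with a two-sided 95% confidence interval for the difference.
2. In the sample-size paragraph, limit the one-sided rationale to POUR incidence, the only outcome it argues for.
3. In the same paragraph, separate the two outcomes that now share the 87%. For length of stay only, give about 80% for a comparison of means, with about 78% (normal data) and about 74% (lower efficiency bound) for the Wilcoxon test.
4. Give duration of POUR its own power figure, based on the expected number of patients with retention, and state the sidedness of its test.

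The cost is wording, plus a fall of about 8 points in the stated power for length of stay. No patients are added and the primary analysis does not change.

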*The following drugs are strong inhibitors of CYP3A4: ketoconazole, itraconazole, clarithromycin, ritonavir, indinavir/ritonavir, lopinavir/ritonavir, and conivaptan.⁴⁸

Randomization:

A consecutive sample of subjects that meet eligibility requirements and give informed consent will be randomized to two study groups via a randomization number generated from a random numbers table. Based on their randomization number patients will be given a prescription (for either tamsulosin or a likeappearing placebo) from the Mayo pharmacy at least one week prior to the date of surgery. The pharmacy will record which group the patient has been assigned to in a central pharmacy database. This database will then be used in the perioperative and postoperative period to maintain the patient's drug designation and administration while in the hospital. The randomization will be blinded to both the treating physician's team and the patient until the end of the study and data analysis is undertaken.

Drug Administration:

In order to achieve full steady state concentrations of the drug by the time of surgery, patients will be instructed to take the assigned drug for 5 days prior to surgery, as well as the morning of surgery. Thus, patients will be given 6 pills of the study medication or the like-appearing placebo at a preoperative clinic visit. On the morning of surgery patients will be admitted to Saint Marys Hospital as morning admissions and proceed to surgery that day based on the surgical schedule. Data on medication compliance will be collected and recorded at that time. Patients will continue taking tamsulosin 0.4mg or like-appearing placebo provided by the Mayo Pharmacy beginning on post-operative day one and continuing every day during their postoperative hospital course until the time of discharge. At that time the primary treating team will write an order to discontinue the study medication. Because each patient will be at therapeutic steady state concentrations of the drug by the time of surgery, shorter hospital stays should not underestimate the potential treatment benefit of this medication. Standard postoperative orders for patients undergoing decompressive cervical or lumbar laminectomy and/or spinal fusion have been in place for neurosurgical patients and will continue to be used during this study (postoperative order set

MC1156-404). The cost of the study medication will be covered by the study and patients will not be charged.

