Patients experiencing possible severe side effects from this medication will be instructed to contact the primary neurosurgical team prior to hospitalization. During hospitalization, any patients experiencing such effects will be immediately evaluated by the neurosurgical team with appropriate intervention or consultation as deemed necessary. The PI or Co-PI will be informed of any serious adverse events thought to be related to medication administration and appropriate steps will be taken to determine whether the adverse event was related to the medication under investigation or other patient medication/condition (e.g. narcotic analgesics, other cardiovascular medication, or dehydration). The decision to stop the study medication will be determined by the primary neurosurgical team responsible for the patient in collaboration with the PI/Co-PI after the seriousness of the event is taken into consideration. All serious adverse events will be reported to the Mayo IRB within 24 hours of the event taking place, and to the FDA if necessary. All major and minor adverse effects of the study medication (tamsulosin or placebo) will be recorded in the medical record and used for data analysis.

Inclusion of Women, Minorities, and Children:

Women will be included in this study. Minorities will be included in the study in the same proportion as they present to the outpatient neurosurgery clinic. Mentally disabled patients, prisoners, and children will be excluded from the study.

References:

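### The protocol promises to record and analyse minor as well as major adverse effects, but describes no active elicitation of non-severe effects during the five days of home dosing

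*Combined protocol and SAP*

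**What the plan says.** **Dosing.** Under Methods, Drug Administration, "patients will be instructed to take the assigned drug for 5 days prior to surgery, as well as the morning of surgery". Six pills are handed out at a preoperative clinic visit, and the patient is admitted on the day of surgery. Of that admission the section says: "Data on medication compliance will be collected and recorded at that time". Dosing then resumes in hospital and runs to discharge: "Patients will continue taking tamsulosin 0.4mg or like-appearing placebo provided by the Mayo Pharmacy beginning on post-operative day one".

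**Commitment.** The Adverse Events section says: "All major and minor adverse effects of the study medication (tamsulosin or placebo) will be recorded in the medical record". The same sentence adds that they will be used in the analysis.

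**Route before admission.** The same section says: "Patients experiencing possible severe side effects from this medication will be instructed to contact the primary neurosurgical team prior to hospitalization". It gives no instruction for effects that are not severe.

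**Other provisions.**
- Adverse Events, on monitoring: "All patients will be regularly monitored with respect to blood pressure, heart rate, and rhythm according to existing standard postoperative procedures".
- Outcome Measures lists adverse events among the items taken from the medical record for all patients, limited to those judged related to study medication.
- Quality Control says that most data come from the electronic record during or shortly after the hospital stay. It directs its particular emphasis on adverse-event reporting to the doctors who look after inpatients after surgery.

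No section describes a diary, telephone call, checklist or admission question about non-severe effects in the home phase.

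**The concern.** The recording commitment has no time limit, but the stated means of meeting it are mostly in-hospital ones. A mild symptom on the second day at home, gone by admission, reaches the medical record only if somebody asks or the patient happens to mention it. Once missed, it cannot be recovered at analysis.

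The home days are informative for tolerability. They include the first exposure to the drug, and they precede anaesthesia, surgery and postoperative analgesia. The Adverse Events section itself names narcotic analgesics and dehydration as competing explanations for an event. Dizziness at home is therefore easier to attribute than dizziness on the ward.

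Tolerability also matters to the trial's argument. The Background expects fewer side effects from a uroselective drug, and the Significance section foresees a possible new standard of care. An under-count of minor effects would make the drug look somewhat better tolerated than it is.

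**Working it through.** The plan gives no figure for adverse-event capture, so there is none to reproduce. The check sets the stated routes against a non-severe effect that starts and ends at home, and then considers scale.

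**1. Would any stated route record it?**
- Patient call before admission (Adverse Events): no, it is for suspected severe effects.
- Data collection at morning admission (Drug Administration): compliance is the only item stated.
- Medical-record review (Outcome Measures): only if the effect has already been entered in the record.
- Vital-sign monitoring (Adverse Events): postoperative.
- Emphasis on adverse-event reporting (Quality Control): for doctors of postoperative inpatients.
- Resumed dosing from postoperative day one (Drug Administration): could reveal an effect that persists or recurs, but not one that has resolved for good.

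None of these asks the patient about it.

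**2. Share of exposure.** Experimental Design gives average participation as 8 to 12 days. If that is counted from first dose (assumption), five home days are 5/12 = 42% to 5/8 = 63% of it.

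**3. Order of size.** The inputs are 175 patients per arm (Analysis of the Data) and two rates from the Adverse Events section. The first is 8.4%: "Abnormal ejaculation was reported in 8.4% of patients taking the 0.4 mg daily dose". The second is 0.2% for orthostatic hypotension.
- Abnormal ejaculation, if the rate applied to everyone: 175 × 0.084 = 14.7. It cannot, because women are enrolled.
- The share of men is not given. Assume 40% to 60%, and that the rate is among men, since the approval is for males. At 40%: 175 × 0.40 = 70, and 70 × 0.084 = 5.9. At 60%: 175 × 0.60 = 105, and 105 × 0.084 = 8.8. That is about 6 to 9 patients in the tamsulosin arm.
- Orthostatic hypotension: 175 × 0.002 = 0.35 expected cases.

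These are possible total events, not missed events. The first range makes no reduction for short exposure, so for a given share of men it is likely to be high. The protocol discounts abnormal ejaculation for two reasons. Short exposure applies to the home days too. The other, "decreased likelihood of sexual activity in the immediate postoperative period", does not.

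**4. Effect on the comparison.** Suppose both arms record the same fraction c of true events, as blinding makes plausible. With true risks pT and pP, the observed difference is c·pT − c·pP = c(pT − pP). The absolute difference shrinks towards zero by the factor c. The ratio (c·pT)/(c·pP) = pT/pP is unchanged, but rests on fewer events. The documents give no basis for a value of c.

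**The case against.** **Silence is not prohibition.** A reader might infer that minor home effects are recorded only if volunteered. The protocol does not say that. It says that compliance data are collected at admission, not that nothing else is. The adverse-event item in Outcome Measures is not restricted to the inpatient period. Ordinary admission history-taking may catch some events. The operations manual announced under Quality Control could hold an admission question, and neither it nor the consent pages are in our copy. This stands, and it limits the point to what the protocol describes.

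**The commitment can be read modestly.** It may mean that effects which come to notice are recorded, not that patients will be questioned. On that reading spontaneous reporting is compatible with it, so this is a gap in method and not a contradiction.

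**Other safeguards exist.** Surgeons and the physician extenders who enrol patients are instructed on risks. Patients are told how to recognise an allergic reaction, and men are warned about priapism. Head nurses are briefed, and contact details for adverse-event reports are issued before the study starts. These help with serious events, but none elicits minor ones.

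**The contrast with the ward is thin.** No structured question on minor effects is stated for the hospital stay either, and ward observation would not reveal abnormal ejaculation. This is fair. The home phase differs in having no daily observation at all.

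**The consequence is small.** This stands too. The plan does not promise separate pre-admission rates, and the sample-size section powers no safety comparison.

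**Conclusion.** The point holds as a low-cost improvement in safety ascertainment. The protocol describes no active elicitation of non-severe effects during home dosing, although it commits to recording and analysing minor effects. Followed as stated, minor effects that resolve before admission would be under-recorded, and any home-phase rates are best read as minimum figures.

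The size of the loss cannot be estimated from the documents. The 6 to 9 patients above only indicate scale, and rest on an assumed share of men and on applying the labelled rate to men without reduction for short exposure. With 0.35 orthostatic cases expected, the gap mainly concerns commoner minor effects.

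Two stronger readings are not supported. One is that the gap biases safety results for or against one arm in particular. Blinding makes similar under-recording in both arms the likelier outcome, with absolute differences shrunk. The other is that efficacy results are compromised. Urinary retention, catheterizations and length of stay are measured in hospital by separate procedures, and the gap does not touch them.

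Confidence is medium, because the operations manual might already supply the missing step.

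**What to change.** When compliance is recorded at the morning admission, have blinded study staff ask every patient a short fixed set of questions: dizziness, fainting, a fall, allergic symptoms, abnormal ejaculation (men), and any doses stopped and why. Record the answers as adverse events from first dose. Tabulate pre-admission and in-hospital events separately by arm, and compare arms within each period, because the two periods are ascertained differently. Keep the instruction to call about severe effects as the urgent route.

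Limit what is passed on. Give the surgical team only safety-relevant answers, such as fainting, a fall, symptomatic hypotension or an allergic reaction, and not abnormal ejaculation or mild transient symptoms. Under Outcome Measures that team decides on indwelling catheters and when they come out, and removal sets time zero for the duration of retention. Hints about allocation should not reach it without need.

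The cost is a few extra questions at an existing contact, more minor and often unrelated events to tabulate, and a small remaining risk of treatment clues. Sample size and efficacy analyses do not change. If the operations manual already contains such a step, one sentence in the protocol is enough.
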